#### Unscheduled Visit – Cellulitis-like Reaction

Subjects reporting signs/symptoms of a Cellulitis-like Reaction between Day 1 and Study Exit Visit will be asked to attend an additional clinic visit within 24 hours (up to 3 days if on a weekend) of the symptoms meeting the definition of a cellulitis-like reaction.

The criteria for a Cellulitis-like Reaction are concurrent presence of all three of the following:

- Grade 3 injection site pain;
- Grade 3 injection site erythema;
- Grade 3 injection site induration.

Investigational site staff attending the subject will confirm if he or she meets or has met the cellulitis-like illness case definition postvaccination according to reported symptoms and, if applicable, will perform other clinical investigations as relevant according to routine clinical practice. Additionally, investigational site staff will assess for the presence of ulceration,

abscess, or necrosis at the injection site, which will inform the application of study enrolment halting rules. In the event of a possible cellulitis-like reaction, sites should identify a local laboratory to perform any laboratory analyses to investigate, confirm, and manage any confirmed cellulitis-like reactions, and document any results in the source notes.

### End of Study - Postvaccination Safety Follow-up Telephone Call (Day 90+7 and 180+7 after Last Vaccination)

Serious adverse events will be collected for at least 180 days after administration of the last vaccination dose. Subjects will be contacted by telephone at 90 (+7) and 180 (+7) days after the last vaccination dose to obtain this information.

### 3.3.4 Schedule of Assessments

Schedule of Assessments – Single Dose Regimen						
Assessment	Pre-Study	Visit 1	Phone call	Visit 2	Phone call	Phone call
	Day -7 to -1	Vaccination	Diaries Reminder	Exit Visit	SAE Follow-up	SAE Follow-up
	Day -7 to -1	Day 1	Day 3 + 2	Day 29 + 4	Day 90 + 7	Day 180 + 7
Invitation to participate		✓ 				
Informed consent		✓ 				
Demographics and influenza vaccination history		✓ 				
Medical history and baseline medication use		✓ 				
Targeted physical examination (if necessary)		✓ 		✓		
Body weight		✓ 				
Axillary temperature		✓				
Review of eligibility criteria		✓				
Blood sample for immunogenicity testing		✓		✓		
Vaccination		✓				
Provision of study supplies and instructions		✓				
Solicited Diary review			✓	✓		
Unsolicited/Concomitant Medications Diary review			✓	✓		
Assessment for cellulitis-like reaction, influenza-like illness (if applicable) 		← ✓ →				
Review of adverse events and concomitant medications	← ✓ →					
Review of SAEs (if applicable)	← ✓ →					

**Notes to the schedule of assessments:**

 These may be performed on or up to 7 days before the day of vaccination.

 Elevated axillary temperature of  $\geq 99.5^{\circ}\text{F}$  ( $\geq 37.5^{\circ}\text{C}$ ) (or a clear history of fever/chills), and at least one respiratory symptom (including sore throat, cough, wheezing, rhinorrhea/rhinitis) and at least one systemic symptom (including myalgia, headache, malaise, nausea and/or vomiting, loss of appetite, and irritability).

Schedule of Assessments – Two Dose Regimen

Assessment		Visit 1	Phone call	Visit 2	Phone call	Visit 3	Phone call	Phone call
	Pre-Study	Vaccination	Diaries Reminder	Vaccination	Diaries Reminder	Exit Visit	SAE Follow-up	SAE Follow-up
	Day -7 to -1	Day 1	Day 3 + 2	Day 29 + 4	Day 3 + 2 after 2 nd dose	Day 29 + 4 after 2 nd dose	Day 90 + 7 after 2 nd dose	Day 180 + 7 after 2 nd dose
Invitation to participate		✓ 						
Informed consent		✓ 						
Demographics and influenza vaccination history		✓ 						
Medical history and baseline medication use		✓ 						
Targeted physical examination (if necessary)		✓ 		✓		✓		
Body weight		✓ 						
Axillary temperature		✓		✓				
Review of eligibility criteria		✓		✓				
Blood sample for immunogenicity testing		✓				✓		
Vaccination		✓		✓				
Provision of study supplies and instructions		✓		✓				
Solicited Diary review			✓	✓	✓	✓		
Unsolicited/Concomitant Medications Diary review			✓	✓	✓	✓		
Assessment for cellulitis-like reaction, influenza-like illness (if applicable) 				✓				
Review of adverse events and concomitant medications				✓				
Review of SAEs (if applicable)					✓			

Notes to the schedule of assessments:  These may be performed on or up to 7 days before the day of vaccination.  Elevated axillary temperature of  $\geq 99.5^{\circ}\text{F}$  ( $\geq 37.5^{\circ}\text{C}$ ) (or a clear history of fever/chills), and at least one respiratory symptom (including sore throat, cough, wheezing, rhinorrhea/rhinitis) and at least one systemic symptom (including myalgia, headache, malaise, nausea and vomiting, loss of appetite, and irritability).

### 3.4 Concomitant Medication

Subjects are not to be enrolled into the study if they receive any prohibited therapy or any therapy in a prohibited dosage that cannot be discontinued or reduced to a permitted dose before enrolment.

The following therapies are NOT PERMITTED before and/or during the active study period (Day 1 to Exit Visit) for the periods outlined below and as specified in the study exclusion criteria:

- Current or recent immunosuppressive or immunomodulatory therapy, as follows:
  - Chronic or long term systemic corticosteroids:  $\geq 0.125$  mg/kg/day of oral prednisolone or equivalent daily;
  - Sporadic systemic corticosteroids:  $\geq 0.5$  mg/kg/day of oral prednisolone or equivalent for one or more short courses of  $> 3$  days in the three months preceding vaccination and/or during the active study period.
- Administration of immunoglobulin and/or any blood products within the 3 months preceding study vaccination, or planned administration during the active study period;
- Participation in a clinical trial or use of an investigational compound (ie, a new chemical or biological entity not licensed for clinical use) within 28 days prior to the first dose of Study Vaccine, or within 28 days after receiving the final indicated dose of Study Vaccine, or plans to enter a clinical trial during this period;
- Vaccination with a licensed or investigational influenza vaccine within the 6 months prior to receiving the first dose of Study Vaccine and during the study;
- Vaccination with a licensed live or inactivated vaccine 21 days prior to receiving the Study Vaccine, or plans to receive any licensed vaccine prior to the Study Exit Visit;

- Treatment with warfarin or other anticoagulants in the 3 weeks preceding vaccination, contraindicating intramuscular vaccination (with the exception of antiplatelet agents).
- Prophylactic antipyretics on the day of vaccination or for the first 7 days postvaccination. Antipyretic use for the treatment of AEs during the study period is permitted, and will be documented as concomitant medications.
- The use of topical anesthetic cream (eg, EMLA Cream) on the vaccination site before or after administration of the Study Vaccine is prohibited. Topical anesthetic cream use at the blood draw site is permitted.

If any of the above therapies are received during the active study period, the subject will not be withdrawn from the study unless required for medical reasons, but immunogenicity results pertaining to this subject may be excluded from assessment prior to unblinding following medical review of the potential for the therapies to impact on immunogenicity results.

### **3.5 Study Analysis Populations**

There will be four analysis populations defined for the study analyses:

#### **3.5.1 Full Analysis Set**

The Full Analysis Set (FAS) will comprise all subjects who provide informed consent and who were randomized to treatment. Screening failures will not be included in the FAS. However, the number of screening failures will be summarized in the disposition tables and all screening failures will be listed.

The FAS will be used to produce summaries and listings of subject characteristics. Subjects will be analysed according to the treatment they were randomised to.

#### **3.5.2 Safety Population**

##### **3.5.2.1 Overall Safety Population**

The Overall Safety Population will comprise all subjects in the FAS who received at least one dose or partial dose of Study Vaccine and have provided any evaluable follow-up safety data.

The Overall Safety Population will be used to produce summaries and listings of overall and unsolicited safety data after any vaccination. Subjects will be analysed according to the treatment they received.

##### **3.5.2.2 Solicited Safety Population**

The Solicited Safety Population will comprise all subjects in the FAS who received at least one dose or partial dose of Study Vaccine and have provided any evaluable data on solicited events.

### 3.5.2.2.1 Solicited Safety Population after the First Vaccination

The Solicited Safety Population after the First Vaccination will comprise all subjects in the FAS who received at least one dose or partial dose of the first vaccination of Study Vaccine and have provided any evaluable data on solicited events after the first vaccination. This safety population will be used in the assessment of solicited AEs after the first vaccination.

### 3.5.2.2.2 Solicited Safety Population after the Second Vaccination

The Solicited Safety Population after the Second Vaccination will comprise all subjects in the FAS who received at least one dose or partial dose of the second vaccination of Study Vaccine and have provided any evaluable data on solicited events after the second vaccination. This safety population will be used in the assessment of solicited AEs after the second vaccination.

### 3.5.2.3 Criteria for Defining Safety Populations

Follow-up safety data is defined as any safety information that is recorded for a subject in a Study Diary or in the subject's medical notes.

The following criteria will be used to define NO follow-up safety data (not included in the Overall Safety Population):

- “Were any unsolicited AEs experienced that were not recorded in the diary?” = BLANK (no entries) AND
- “Were any new SAEs reported?” (Day 90 & 180) = BLANK AND
- “Was the subject confirmed to have experienced symptoms meeting cellulitis-like reaction criteria?” = BLANK AND
- Any AE/SAE form = BLANK AND
- Unsolicited Diary Other Body Symptoms = BLANK (no entries) AND
- Solicited Diary Local Symptoms= BLANK (all 7 days after first and second vaccination) AND
- Solicited Diary Temperature= BLANK (all 7 days after first and second vaccination) AND
- Solicited Diary Systemic Symptoms = BLANK (all 7 days after first and second vaccination)
- Site Entered Local Symptoms = BLANK (all 7 days after first and second vaccination) AND
- Site Entered Temperature= BLANK (all 7 days after first and second vaccination) AND

- Site Entered Systemic Symptoms = BLANK (all 7 days after first and second vaccination)

The following criteria will be used to define subjects with follow-up safety data (included in the Overall Safety Population):

- “Were any unsolicited AEs experienced that were not recorded in the diary?” = YES OR
- “Were any unsolicited AEs experienced that were not recorded in the diary?” = NO OR
- “Were any new SAEs reported?” = YES (Day 90 & 180) OR
- “Were any new SAEs reported?” = NO (Day 90 & 180) OR
- “Was the subject confirmed to have experienced symptoms meeting cellulitis-like reaction criteria?” = YES OR
- “Was the subject confirmed to have experienced symptoms meeting cellulitis-like reaction criteria?” = NO OR
- Any AE/SAE form = ANY FIELD HAS DATA OR
- Unsolicited Diary Other Body Symptoms = ANY FIELD HAS DATA (on any of the 28 days) OR
- Solicited Diary Local Symptoms= ANY FIELD HAS DATA (on any of the 7 days after first or second vaccination) OR
- Solicited Diary Temperature= ANY FIELD HAS DATA (on any of the 7 days after first or second vaccination) OR
- Solicited Diary Systemic Symptoms = ANY FIELD HAS DATA (on any of the 7 days after first or second vaccination)
- Site Entered Local Symptoms= ANY FIELD HAS DATA (on any of the 7 days after first or second vaccination) OR
- Site Entered Temperature= ANY FIELD HAS DATA (on any of the 7 days after first or second vaccination) OR
- Site Entered Systemic Symptoms = ANY FIELD HAS DATA (on any of the 7 days after first or second vaccination)

The following criteria will be used to define NO safety data on solicited events (not included in the Solicited Safety Population):

- Solicited Diary Local Symptoms= BLANK (all 7 days after first and second vaccination) AND
- Solicited Diary Temperature= BLANK (all 7 days after first and second vaccination) AND

- Solicited Diary Systemic Symptoms = BLANK (all 7 days after first and second vaccination)
- Site Entered Local Symptoms = BLANK (all 7 days after first and second vaccination) AND
- Site Entered Temperature= BLANK (all 7 days after first and second vaccination) AND
- Site Entered Systemic Symptoms = BLANK (all 7 days after first and second vaccination)

The following criteria will be used to define subjects with safety data on solicited events (included in the Solicited Safety Population):

- Solicited Diary Local Symptoms= ANY FIELD HAS DATA (on any of the 7 days after first or second vaccination) OR
- Solicited Diary Temperature= ANY FIELD HAS DATA (on any of the 7 days after first or second vaccination) OR
- Solicited Diary Systemic Symptoms = ANY FIELD HAS DATA (on any of the 7 days after first or second vaccination)
- Site Entered Local Symptoms= ANY FIELD HAS DATA (on any of the 7 days after first or second vaccination) OR
- Site Entered Temperature= ANY FIELD HAS DATA (on any of the 7 days after first or second vaccination) OR
- Site Entered Systemic Symptoms = ANY FIELD HAS DATA (on any of the 7 days after first or second vaccination)

The criteria used to define Solicited Safety Population, limited to the first vaccination data, will be used to define subjects with safety data on solicited events after the first vaccination. The (additional) following criteria to those noted above will be applied

- Did subject receive the vaccination? = Yes

The (additional) following criteria to those noted above will be used to define subjects with safety data on solicited events after the second vaccination

The criteria used for Solicited Safety Population, limited to the second vaccination data, will be used to define subjects with safety data on solicited events after the second vaccination. The (additional) following criteria to those noted above will be applied

- Dose Group= Two Doses
- Did subject receive the vaccination? = Yes (for both doses)

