### 3.5.4 Per-Protocol Population

The Per-Protocol Population (PPP) will comprise all subjects in the Evaluable Population who do not have any protocol deviations that were medically assessed as potentially impacting on immunogenicity results.

The Per Protocol Population will be the primary population of interest for the primary immunogenicity analysis and a supporting analysis will be performed using the Evaluable Population.

Membership of the PPP will be determined prior to unblinding the study.

Primary and secondary immunogenicity analyses will be completed using the Per-Protocol Population. Duplicate tables of primary and secondary immunogenicity analyses may also be produced based on the Evaluable population if there is >1% difference in the total number of subjects in either of the two age-strata (6 through 35, and 36 through 59 months) between the Per-Protocol Population and the Evaluable Population. The decision to produce tables based on the Evaluable Population will be made by Seqirus after population sets are finalised and prior to unblinding. Analysis on antipyretics frequency will be performed on the Per-Protocol Population.

The study biostatistician will provide information on proposed datasets to Seqirus for review. Protocol deviation listings will also be reviewed by Seqirus prior to the finalisation of the population datasets, which will occur prior to unblinding. The lists will be used to determine which subjects should be excluded from either the Evaluable or the Per Protocol Population, with documentation of the reason for exclusion.

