#### 4.7.4.4 Unsolicited Adverse Events

Unsolicited AEs will be coded using MedDRA v19. The number (and percentage) of subjects experiencing at least one event (ie, the incidence) of unsolicited AEs will be summarized by MedDRA system organ class (SOC) and preferred term (PT), overall and by maximum intensity. For summaries by maximum intensity, if a subject experiences more than one event in the same system organ class and preferred term, the event with the maximum intensity will be summarised. Maximum intensity will be ranked as follows: severe > moderate > mild > unknown. All summaries will be presented by treatment group (i.e. Seqirus QIV/Comparator QIV/Overall), and repeated by age strata, gender, race, and ethnicity where specified.

Summaries will be presented for:

- Any AEs
- Any AEs by maximum intensity
- Any AEs by relationship to Study Vaccine
- Any SAEs
- Any discontinuations due to AEs
- Any deaths
- Any AESIs

All tables listing events by MedDRA SOC will use the internationally agreed order of MedDRA SOCs:

- Infections and infestations
- Neoplasms benign, malignant and unspecified (incl cysts and polyps)
- Blood and lymphatic system disorders
- Immune system disorders
- Endocrine disorders
- Metabolism and nutrition disorders
- Psychiatric disorders

- 
- Nervous system disorders
  - Eye disorders
  - Ear and labyrinth disorders
  - Cardiac disorders
  - Vascular disorders
  - Respiratory, thoracic and mediastinal disorders
  - Gastrointestinal disorders
  - Hepatobiliary disorders
  - Skin and subcutaneous tissue disorders
  - Musculoskeletal and connective tissue disorders
  - Renal and urinary disorders
  - Pregnancy, puerperium and perinatal conditions
  - Reproductive system and breast disorders
  - Congenital, familial and genetic disorders
  - General disorders and administration site conditions
  - Investigations
  - Injury, poisoning and procedural complications
  - Surgical and medical procedures
  - Social circumstances
  - Product issues

Only treatment emergent AEs (commencing after exposure to study treatment) will be included in the unsolicited AE and SAE summaries. Non-treatment emergent events (starting prior to exposure to study treatment) will be included in the subject listings and flagged but not included in the above summaries. Where an AE start date is partially or fully missing, and it is unclear as to whether the AE is treatment emergent, it will be assumed that it is.

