All the AEs starting on the day of or before the exit visit (Day 29 + 4) will be included in the summaries of unsolicited AEs. AEs starting after the exit visit will be included in the subject listings and flagged but not included in the above summaries. Where an AE start date is partially or fully missing, and it is unclear as to whether the AE starts prior to the exit visit, it will be assumed that it does.

In the interim analysis, SAEs started after the exit visit will be excluded from the analysis. SAEs up to day of the safety follow-up call, irrespective of the date will be included in the final safety analysis.

If sufficient numbers of cases of AEs occur, more formal statistical analyses of event rates, duration or severity may be conducted.

Deaths will be presented by time period (Day 1 to Study Exit Visit, and Day 1 to Day 180 after last vaccination dose), by treatment, subject number, preferred term, and relationship.

All other AE information collected (e.g. outcome, action taken) will be listed as appropriate.

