### 5.3 Tables

Tables based on the Evaluable Population will be conducted, depending on the difference in absolute numbers of subjects between the two populations (see [Section 3.5.4](#)).

All Tables and Listings will be produced for the interim analysis after Study Exit Visit. If there are no events to summarise in a table/listing, the output will be produced displaying a message, for e.g. 'There were no xxxx events recorded'. Flagged (\*) Tables and Listings will be repeated for the final analysis. Flagged (\*\*) Tables and Listings will be produced for the final analysis only.

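### One answer at a Day 90/180 SAE call puts a child in the unsolicited AE denominator with no Day 1-to-Exit AE information, biasing that rate slightly low

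*SAP*

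**What the plan says.** **Membership.** SAP 3.5.2.3 gives two mirrored lists. A child is left out of the Overall Safety Population only if every listed field is empty, including "Were any new SAEs reported?” (Day 90 & 180) = BLANK AND". A child is included if any one field is filled, and one such line is "Were any new SAEs reported?” = NO (Day 90 & 180) OR". Another line accepts any AE/SAE form holding data, with no limit on onset; Protocol 9.4 starts AE recording at consent. The calls themselves collect SAEs (SAP 3.3.3) or SAEs and AESIs (Protocol 8.4.4), not non-serious events.

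**Use.** SAP 3.5.2.1: "The Overall Safety Population will be used to produce summaries and listings of overall and unsolicited safety data after any vaccination".

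**Statistic.** SAP 4.7.4.4 summarises "The number (and percentage) of subjects experiencing at least one event (ie, the incidence) of unsolicited AEs". On the window it says: "All the AEs starting on the day of or before the exit visit (Day 29 + 4) will be included in the summaries of unsolicited AEs". Events starting before vaccination are listed but not counted. SAP 4.11 covers titers below 10 and partly missing solicited entries; it has no rule for absent unsolicited follow-up.

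**Timing.** SAP 3.5.4 states: "Protocol deviation listings will also be reviewed by Seqirus prior to the finalisation of the population datasets, which will occur prior to unblinding". SAP 4.10.1 repeats this. SAP 5.3 says that flagged "Tables and Listings will be repeated for the final analysis", and the unsolicited AE tables by system organ class and by age stratum carry that flag.

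**The concern.** One population serves two follow-up windows. An answer about SAEs at Day 90 or Day 180 is proper evidence of follow-up for the SAE, AESI and death tables. It says nothing about non-serious events between vaccination and the Exit Visit, yet it puts the child in the denominator for those events. With no other denominator and no missing-data rule, the child is counted as having had none.

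The frequency of unsolicited AEs is a secondary safety endpoint, and this rule pushes it in one direction, downwards. The SAP matches population to window for solicited events by defining separate sets after the first and second vaccination, but does not do so here. The SAP also leaves open when safety membership is settled, so the interim and final reports could divide the same Day 1-to-Exit events by different numbers.

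**Working it through.** **The plan's own figure.** 2000 evaluable with 10% dropout: 2000 / (1 - 0.10) = 2222.2, which the plan prints as 2222. It is used here only to turn shares into children. The plan gives neither the share of children without Day 1-to-Exit AE information nor an expected unsolicited AE rate, so both are assumptions below.

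**Step 1: who gets in.** Apply the OR list in SAP 3.5.2.3, then the counting rule in SAP 4.7.4.4.

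| Only record after enrolment | In the set? | Unsolicited AE information, vaccination to Exit | Counted as |
|---|---|---|---|
| SAE question answered NO at a call | yes | none | event-free |
| AE form, onset before vaccination | yes | none | event-free (the event is excluded) |
| One solicited diary or site entry | yes | none | event-free |
| Answer to the cellulitis question | yes | none | event-free |
| Nothing at all | no | none | not counted |

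The first two rows are the clearest mismatch, because the record lies wholly outside the window. The next two show that deleting the call lines alone would not cure it.

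**Step 2: size.** Let p be the true incidence among children who were ascertained, and s the share of the set with no ascertainment. Printed rate = p x (1 - s). Taking the set as about 2222, s = 0.5% is 11 children and s = 3% is 67.

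- p = 40%: 0.40 x 0.995 = 39.8%; 0.40 x 0.97 = 38.8%.
- p = 30%: 0.30 x 0.995 = 29.85%; 0.30 x 0.97 = 29.1%.
- Extreme bound, s equal to the full planned dropout of 10%: 0.40 x 0.90 = 36.0%; 0.30 x 0.90 = 27.0%.

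Between arms the factor is (1 - s1) / (1 - s2). Equal shares give 1, so nothing changes. Shares of 2% and 1% would give 0.98 / 0.99 = 0.99.

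**Step 3: when membership can be known.** Protocol 3.3 caps the study at 10 months, about 304 days from first screening to last call. The last dose is then given by day 304 - 187 = 117 to 304 - 180 = 124, and the last Exit Visit falls between day 117 + 28 = 145 and day 124 + 32 = 156. The earliest Day 180 call is at day 180. So no Day 180 answer exists when the last child exits, though some Day 90 answers may. SAP 1 and 4.2 limit the interim analysis to Day 1-to-Exit data in any case. Two readings remain:

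- *Membership is derived again at the final analysis.* The denominator can stay the same or grow, while non-serious events in the window are already closed. The disposition table, which shows the size of each population, is not flagged for repetition, so a changed N would appear without explanation.
- *Membership is frozen before interim unblinding on Day 1-to-Exit data.* The call lines then admit nobody, and a child whose first safety record is a later call is also missing from the SAE denominator, which defeats the purpose of those lines.

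The SAP does not say which applies, nor whether the bracketed Day 90 and Day 180 means either call or both.

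**The case against.** The strongest reply is that Protocol 11.2.2 defines a single Safety Population, based on any evaluable follow-up safety data, for all safety output. On this view SAP 3.5.2.3 merely puts that into practice. The overall and unsolicited summaries also carry SAEs, AESIs and deaths, for which a call answer is genuine follow-up. This stands as a reason to keep the broad set for those rows. It does not justify using it for non-serious events in a window that the call does not cover.

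A second reply is that few children are affected: diaries, site entries, the unsolicited AE question and the cellulitis question must all be blank, yet the family is reached by phone. Protocol 4.2.2 also asks for every effort to complete safety assessments after withdrawal. That is fair, and it is why the size is put as small.

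Three stronger readings are tempting but not supported.

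- *That the denominator does change after interim unblinding.* SAP 3.5.4 and 4.10.1 say population datasets are finalised before unblinding, and nothing provides for deriving the safety set again. Those sentences mainly concern the Evaluable and Per-Protocol sets, so growth is possible but not stated.
- *That the rule works differently by age stratum at the interim, because the older cohort enrols first and has more Day 90 answers.* SAP 1, 4.2 and 4.7.4.4 confine the interim to data up to the Exit Visit, which puts those answers outside it for both cohorts.
- *That a planned treatment comparison is distorted.* SAP 4.7.4.4 plans no relative risk for unsolicited AEs, only possible further analyses if events are numerous. The relative risks in SAP 4.7.4.2 are for solicited AEs, whose populations do not use the call. Parents are blinded, and nothing in the documents suggests that loss differs by arm.

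**Conclusion.** The point holds for the unsolicited AE denominator. The SAP's criteria admit children with no AE ascertainment between vaccination and the Exit Visit, and the tables then count them as event-free. The direction of bias is certain if any such child is admitted. The size is not known: on an assumed share of 0.5% to 3%, a true 40% loses 0.2 to 1.2 percentage points. This is a small distortion of a descriptive secondary safety percentage, with no bearing on the co-primary endpoints or the sample size.

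The timing element is a missing statement. No freeze is given specifically for the safety set, so its size could grow between the interim and final reports.

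**What to change.** 1. For the Day 1-to-Exit unsolicited AE tables, define a set that requires AE ascertainment between vaccination and the Exit Visit: an answer, YES or NO, to the unsolicited AE question, or any entry in the Other Body Symptoms Diary. Do not admit a child on a Day 90/180 answer, a pre-vaccination AE form, or solicited or cellulitis data alone. Admission must not depend on having had an event: dropping the NO answers while keeping event forms would bias the rate upwards. For the same reason, confirm that a symptom-free day leaves a record in that diary; if it does not, an entry there is itself an event.
2. Keep the present broader set, with the call answers, for the SAE, AESI and death tables, so that an in-window SAE first reported by phone is still counted there.
3. State whether the Day 90/180 criterion means either call or both. Fix the Day 1-to-Exit set before interim unblinding and reuse it unchanged at the final analysis.
4. Record the split in SAP 4.13 as a change from Protocol 11.2.2.

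The cost is SAP wording and one more population flag. Denominators become slightly smaller and printed AE rates slightly higher.
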